### 6.12.7 Change in EoE Endoscopic Reference Score

Change in EREFS from baseline to Week 24 will be analyzed using ANCOVA with age strata, treatment, and baseline EREFS.

The EREFS is the sum of 5 components with a maximum score of 9 for each location (proximal and distal esophagus) and maximum combined score of 18. Individual component score ranges are as follows:

- Edema 0–1
- Rings 0–3
- Exudates 0–2
- Furrows 0–2
- Stricture Range 0–1

Each component is scored based on the presence and/or grade of each feature. Miscellaneous features will not be included in the total score.

Improvements in inflammatory and remodeling features may also be reported based on individual scores for edema, rings, furrows, exudate, and stricture.

Inflammatory and fibrostenotic subscores will be generated (proximal, distal, and combined). The inflammatory subscore is the sum of the exudate, edema, and furrows scores (range 0–5). The fibrostenotic subscore is the sum of the rings and stricture scores (range 0–4).

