10.2 Stratification and Randomization

To be randomized into the study, a subject must meet all inclusion criteria and no exclusion criteria. Subjects will be randomized through the IRT system.

If the subject qualifies for the study after completing all screening procedures, on the day of first infusion (Study Day 1), the site will access the IRT system in order to randomize and stratify the subject in the study and enter the current body weight for study drug dose calculation. Subjects will be stratified at randomization based on age (12–17 and ≥ 18 years) and baseline DSQ score (≤ 30 and > 30). The IRT system will randomly assign the subject to a low dose AK002 regimen (6 doses of 1 mg/kg), a high dose AK002 regimen (first dose at 1 mg/kg, subsequent 5 doses at 3 mg/kg), or placebo in a double-blind approach and will email the kit (vial) number to the study pharmacist.

Approximately 300 subjects with symptomatic EoE will be randomized 1:1:1 to receive 1 of 3 dose regimens in a double-blind fashion: 100 subjects will be randomized to the low dose regimen (1 mg/kg AK002 administered every 4 weeks for 6 doses); 100 subjects will be randomized to the high dose regimen (1 mg/kg AK002 for the first dose followed by 3 mg/kg AK002 administered every 4 weeks for the 5 subsequent doses); and 100 subjects will be randomized to placebo. A subject is considered enrolled in the study when the subject is randomized.

For subsequent infusions on Days 29, 57, 85, 113, and 141, the site will access the IRT system on the day of infusion and enter the PID as well as the subject's body weight, and the system will assign the vial(s) on the dose regimen associated with the randomization number. The study pharmacist will then receive an email detailing the kit (vial) number to prepare.

Prior to each infusion, the Investigator or designee will confirm that the PID recorded on the IV bag provided by the study pharmacist matches the subject. The subject's identification should be confirmed and documented by a second party prior to administering the infusion, whenever possible.

The assignment of treatments to AK002 or placebo will be securely retained in the IRT system until such time as designated by the Statistical Analysis Plan.

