15.7.2 Secondary Efficacy Endpoint Analysis

The percent change in peak esophageal intraepithelial eosinophil count at Week 24 will be analyzed using ANCOVA with treatment as a factor and baseline eosinophil counts, baseline DSQ, and age strata as covariates. The LSM, SE, and 95% CI for individual treatment groups, and the LSM, SE, 95% CI, and p-value for the between treatment difference will be presented.

Proportion of subjects achieving peak esophageal intraepithelial eosinophil count of ≤ 1 eosinophil/hpf at Week 24 will be analyzed using Fisher's exact test.

Proportion of subjects achieving peak esophageal intraepithelial eosinophil count of < 15 eosinophil/hpf at Week 24 will be analyzed using Fisher's exact test.

Proportion of Treatment Responders, defined by subjects with $\geq 30\%$ improvement in DSQ score at Weeks 23–24 and a peak esophageal intraepithelial eosinophil count of ≤ 6 eosinophils/hpf at Week 24, will be analyzed using Fisher's exact test.

Proportion of subjects with $> 50\%$ reduction in DSQ score from Baseline to Weeks 23–24 will be analyzed using the Cochran-Mantel-Haenszel (CMH) test. The randomization stratum (age and baseline DSQ) will be used as the stratification factor for the analysis.

Change in DSQ scores from Baseline to Weeks 23–24 will be analyzed using MMRM and will include fixed effects for age, baseline DSQ, treatment, visit, treatment-by-visit interaction, and allow for random subject effects.

The analysis of change in biweekly mean DSQ over time will employ MMRM similarly as described above.

Change in EoE Reference Score for Endoscopic Abnormalities from Baseline will be summarized and analyzed using MMRM with age, treatment, visit, and treatment-by-visit interaction as fixed factors and baseline peripheral blood eosinophil count and baseline DSQ (continuous) as covariates.

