### 5.3 Adjustment for Covariates

Efficacy analyses will be adjusted for baseline values and randomization stratum using analysis of covariance (ANCOVA), mixed model for repeated measures (MMRM), or Cochran-Mantel-Haenszel (CMH) tests, where applicable.

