### **6.12 Analysis of Secondary Efficacy Endpoints**

#### **6.12.1 Percent Change in Tissue Eosinophil Count**

The percent change in peak esophageal intraepithelial eosinophil count at Week 24 will be analyzed using ANCOVA with treatment as a factor, baseline eosinophil counts and age strata as covariates. The LSM, SE, and 95% CI for individual treatment groups and the LSM, SE, 95% CI, and p-value for the between treatment difference will be presented.

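### The ANCOVAs for EREFS change and percent change in eosinophils adjust for age but omit baseline DSQ, the other randomisation factor, which may make these tests slightly conservative

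*SAP*

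**What the plan says.** Protocol 10.2 gives the randomisation factors: "Subjects will be stratified at randomization based on age (12–17 and ≥ 18 years) and baseline DSQ score", with the DSQ split at 30.

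SAP 5.3 gives the general rule: "Efficacy analyses will be adjusted for baseline values and randomization stratum". It names ANCOVA, MMRM and CMH as the methods and limits the rule to where it is applicable.

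The two models at issue are:

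- EREFS change (SAP 6.12.7): "Change in EREFS from baseline to Week 24 will be analyzed using ANCOVA with age strata, treatment, and baseline EREFS".
- Percent change in peak eosinophil count (SAP 6.12.1): "ANCOVA with treatment as a factor, baseline eosinophil counts and age strata as covariates".

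For percent change, Protocol 15.7.2 specified "ANCOVA with treatment as a factor and baseline eosinophil counts, baseline DSQ, and age strata as covariates", and the protocol synopsis agrees. For EREFS, Protocol 15.7.2 specified an MMRM with baseline DSQ and baseline peripheral blood eosinophil count among the covariates. The synopsis instead refers EREFS to an MMRM described earlier and does not clearly list baseline DSQ for it. SAP section 1 says that the SAP supersedes the protocol's statistical methods, so the models without baseline DSQ are the ones that would be run.

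SAP Table 7 places EREFS at step 6 (high dose) and step 13 (low dose), and percent change in eosinophils at steps 7 and 14. The low-dose co-primaries are step 8. Under SAP 5.8 each step is tested only if the one before it is significant at the two-sided 0.05 level.

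**The concern.** Stratified randomisation balances the arms on the stratum. A model without the stratum leaves whatever variation it explains in the residual. The reported standard error then does not reflect the precision that the design has bought, and the test is conservative.

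Both ANCOVAs already contain one of the two stratification factors. The DSQ co-primary (SAP 6.11.4), percent change in DSQ (6.12.5), the MMRM (6.12.6) and the CMH test for >50% DSQ reduction (6.12.4) all use baseline DSQ, so these two ANCOVAs are the exceptions among the model-based or stratified tests in the hierarchy. The SAP gives no reason, although Protocol 15.1 says that the SAP will detail modifications.

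Power at a gating step is at stake. If high-dose EREFS or high-dose percent change narrowly misses, the low-dose co-primaries are never formally tested. There is also a specification problem: SAP 5.3 and the detailed sections can be read as different models for the same confirmatory step.

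**Working it through.** **The plan's own figure.** The documents give a sample size for the co-primaries only. For DSQ (difference 7.5, SD 15, two-sided 0.05, 90% power): n = 2 × (1.96 + 1.2816)² × 15² / 7.5² = 84.1, so 85 per group. The t-distribution version gives 86 (power 0.903), which matches SAP 3.6, and 86 / (1 − 0.14) = 100 also matches. No effect size, SD or power is given for EREFS or for percent change in eosinophils.

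**Inputs for the check.** n = 86 evaluable per arm (SAP 3.6). r is the partial correlation of baseline DSQ with the outcome, given treatment, age and the endpoint's own baseline. It is not in the documents, and the range 0 to 0.3 is an assumption. The effect δ = 0.4 residual SD is also an assumption.

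**Formulas**, taking the DSQ effect to act through the balanced stratum, with s = √(2/86) = 0.1525:

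- Reported SE without DSQ, relative to with DSQ: 1/√(1 − r²).
- Actual two-sided error without DSQ: 2[1 − Φ(1.96/√(1 − r²))].
- Power without DSQ: Φ[(δ − 1.96s)/(s√(1 − r²))].
- Power with DSQ: Φ[δ/(s√(1 − r²)) − 1.96].

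| r (assumed) | SE ratio | Actual error without DSQ | Power without, δ = 0.4 | Power with, δ = 0.4 | Loss (points) |
|---|---|---|---|---|---|
| 0 | 1.000 | 0.050 | 74.6% | 74.6% | 0 |
| 0.1 | 1.005 | 0.049 | 74.7% | 75.1% | 0.3 |
| 0.2 | 1.021 | 0.045 | 75.1% | 76.3% | 1.3 |
| 0.3 | 1.048 | 0.040 | 75.6% | 78.5% | 2.9 |

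**Larger effects.** With r = 0.3 the same formulas give 98.1% without and 98.5% with DSQ at δ = 0.6, and 99.97% and 99.98% at δ = 0.8. The loss almost disappears once the effect is large.

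**Simulation cross-check.** Three arms, 86 per arm, blocks stratified on a DSQ split, and DSQ acting on a continuous scale. Without DSQ in the model, the simulated type I error was 0.054, 0.050 and 0.036 for r = 0, 0.2 and 0.3. With 3,000 trials each, the Monte Carlo error is √(0.05 × 0.95/3,000) = 0.004, so there is no sign of inflation. At r = 0.3, with an effect set for about 90% power when adjusted, simulated power was 87.8% without DSQ, 89.4% with the stratum and 90.2% with continuous DSQ (1,500 trials).

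**The case against.** Four points can be made for the plan.

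First, SAP 5.3 is qualified, and the SAP does not adjust everywhere: the first co-primary and three secondary endpoints use an unadjusted Fisher's exact test. This stands as a description, but it does not cover these two models. ANCOVA is a method that 5.3 names, and both models already carry half of the stratum. For Fisher's test on the co-primary, SAP 6.11.2 gives a reason; here there is none.

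Second, the protocol is not a clean benchmark for EREFS. Section 15.7.2 and the synopsis differ. The SAP's move from an MMRM to an ANCOVA on baseline EREFS is sensible with a single scheduled post-baseline endoscopy in the double-blind period. This stands. The point is only the missing DSQ term, not the choice of ANCOVA or of baseline EREFS.

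Third, a reader might infer that all four steps use oversized standard errors. The documents do not support that as a fact. DSQ is a symptom score, the endpoints are endoscopic and histologic, and no correlation is given. At r = 0 nothing is lost.

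Fourth, a reader might infer that low-dose testing is materially threatened at both step 6 and step 7. For percent change in eosinophils this is unlikely. SAP 3.6 assumes 90% versus 10% histologic response. Protocol 2.3 reports a 95% mean reduction versus no change, and 13 of 14 versus 1 of 11 responders. Step 7 is also reached only after the high dose has succeeded on histology at steps 1 and 2.

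**Conclusion.** The omission is real and unexplained: both ANCOVAs leave out a randomisation factor, contrary to the general rule in SAP 5.3 and to Protocol 15.7.2. Its consequence is conditional and modest. If baseline DSQ is prognostic beyond age and the endpoint's own baseline, the tests are slightly conservative, by 0 to about 5% of the standard error and 0 to about 3 power points. Those figures rest on an assumed r of 0 to 0.3 and an assumed 0.4 SD effect with 86 per arm. The omission does not inflate type I error, so it is no threat to the validity of a positive result.

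The practical gain is mainly for EREFS, for which the documents give no expected effect or variance. There, step 6 stands before the low-dose co-primaries. For percent change in eosinophils the reason to change is mostly consistency.

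**What to change.** Before unblinding, add baseline DSQ to the models in SAP 6.12.1 and 6.12.7, either as a continuous covariate or as the ≤30/>30 stratum, and state which. Keep baseline eosinophil count and baseline EREFS as they are. If the omission is deliberate, give the reason in the SAP, as is done for Fisher's exact test.

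The cost is one degree of freedom per model. Baseline DSQ is already collected and used for randomisation, so no new data are needed. The change also leaves a single specification for each of steps 6, 7, 13 and 14.

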### 6.13 Analysis of Exploratory Endpoints

Change in continuous exploratory endpoints collected at multiple post-baseline time points will be analyzed using MMRM and will include fixed effects for age, baseline value, treatment, visit, and the treatment-by-visit interaction and allow for random subject effects. Treatment and week will each be fitted as categorical variables. The model will assume unstructured covariance structure.

#### 6.13.1 Change in CCI [REDACTED]

Change in the following components of the CCI [REDACTED] from baseline to Week 24 will be reported in a descriptive manner:

- CCI [REDACTED]

Change in the following components of the CCI [REDACTED] from baseline to Week 24 may be assessed post-database lock in addition to calculation of a total CCI [REDACTED] score:

- CCI [REDACTED]

### 6.13.2 Change in CCI

Change from baseline in CCI summary (including Domain) scores will be analyzed using CCI baseline CCI value as covariate, and subject as repeated measure unit over visits.

### 6.13.3 Change in CCI

Change from baseline in the number of CCI will be analyzed using CCI and baseline CCI as covariate.

### 6.13.4 CCI

Methods for CCI and CCI analysis are described in a separate analysis plan.

## 6.14 Analysis of Pharmacokinetic Endpoint

The analysis of the PK concentration will be based on the Safety population. AK002 concentrations will be listed by treatment, subject, nominal time, and actual time. Concentrations that are BLOQ (below limit of quantification) will be indicated in the listing.

Plasma concentrations will be summarized at each nominal time point separately for each treatment. The following descriptive statistics will be presented: n, arithmetic mean, SD, geometric mean, % CV, median, minimum, and maximum.

Individual plasma concentration vs. actual times will be plotted for each subject in linear and semi-logarithmic scales, placed on the same page. Mean plasma concentration at the scheduled time points will be plotted for each treatment in linear and semi-logarithmic scale, with the associated SE (for linear scale only) at each scheduled time point.

In the plot, concentrations that are BLOQ will be assigned a value of 0 if they are collected predose or assigned a value of half the LLOQ (lower limit of quantification) if they are collected postdose.

Analysis of PK parameters are specified separately in a PK analysis plan.

## 6.15 Safety Analyses

### 6.15.1 Adverse Events

Safety assessments will be based mainly on the nature, frequency, relationship, and severity of the AE, and AE will be coded by primary SOC and PT according to MedDRA (version 21.0).

The treatment-emergent adverse events (TEAE) will be summarized by the number and percentage (n and %) of subjects in each SOC and PT.

For summaries by relationship to study drug, “possibly related” will be combined with “related”, and “unlikely/remotely related” will be combined with “not related.” When multiple AE are reported with the same PT, the AE of the strongest relation to study drug will be included in the summary by relationship, and the AE of the most severe grade will be included in the summary by severity table.

The following AE incidence tables will be presented.

- Overview of TEAE to include
  - Number (%) of subjects who reported at least 1 TEAE
  - Number (%) of subjects who reported at least 1 treatment-related TEAE
  - Number (%) of subjects who reported at least 1 severe TEAE
  - Number (%) of subjects who reported at least 1 serious TEAE
  - Number (%) of subjects who reported at least 1 TEAE leading to treatment discontinuation
  - Number (%) of subjects who reported at least 1 TEAE leading to study discontinuation
  - Number (%) of subjects who reported at least 1 TEAE of special interest (TEAESI)
- TEAE by PT sorted by decreasing order of subject incidence in the combined treatment group
- TEAE by SOC and PT in alphabetical order
- TEAE by SOC, PT, and maximum severity
- TEAE by SOC, PT, and strongest relationship to study drug
- TEAE leading to treatment discontinuation by SOC and PT, if warranted by sample size
- TEAE leading to study discontinuation by SOC and PT, if warranted by sample size
- Serious TEAE by SOC and PT, if warranted by sample size
- TEAESI by SOC and PT

All AE will be listed with onset/stop day, relationship to study drug, severity, action taken, and outcome. Pertinent subject information including treatment group and demographics will also be included.

Separate listings will be provided for TEAE leading to study discontinuation, TEAESI, and treatment-emergent SAE (TESAE).

### **6.15.2 Laboratory Test**

Laboratory data will be summarized by presenting summary statistics of raw data and change from baseline values (means, medians, SD, ranges). For quantitative laboratory parameters, both actual values and change from baseline values will be summarized at each visit.

Shift tables will be presented in which lab test results at baseline and post-baseline visits will be classified into below ( $< LLN$ ), within ( $\geq LLN$  and  $\leq ULN$ ), and above ( $> ULN$ ) normal ranges. Subject incidences (n and %) will be presented for the shift from baseline to the post-baseline visits.

*Note:* Analysis window will be applied for the visits.

A complete laboratory data listing including hematology, biochemistry, and urinalysis will be provided for all subjects.

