Post-Dose Observation ²⁹		X			X	X	X	X	X			
Symptom-Directed Physical Exam ³⁰		X ¹		X ¹	X ¹	X ¹	X ¹	X ¹	X ¹	X ¹	X ¹	
Prior and Concomitant Medications	X	X	X	X	X	X	X	X	X	X ³⁴	X	
Adverse Events ³¹	X	X	X	X	X	X	X	X	X	X	X	X
Open-Label Extended Dosing ³⁴										X ³⁴	X ³⁴ – Day 197 visit does not apply to subjects in OLE period	

ADA: Anti-drug Antibody

ET: Early Termination

FSH: Follicle-Stimulating Hormone

IP: Investigational Product

CBC: Complete Blood Count

ECG: Electrocardiogram

hCG: Human Chorionic Gonadotropin

PK: Pharmacokinetics

DSQ: Dysphagia Symptom Questionnaire

EGD: Esophago-gastro-duodenoscopy

IRT: Interactive Response Technology

Table 1 Notes

- 1) Refer to assessment footnote for specific time points (e.g., predose, during infusion, postdose) to conduct the assessment on dosing days.
- 2) The screening period (Baseline) assessments can be conducted over multiple days within the screening period. The screening period must be a minimum of 14 days (2 weeks) and no longer than 60 days (or a maximum of 35 days after the Screening EGD, whichever is shorter). Day 1 can begin as soon as eligibility criteria are met.
- 3) Fecal collection kits for Ova and Parasite will be provided to subjects at the time of consent. Stool sample should be returned to the clinical site within 24 hours of collection.
- 4) At the time of consent, the Study Coordinator will activate all ePRO questionnaires in EDC, provide the subject with a unique username and password, train the subject on daily DSQ ePRO completion and compliance, and ensure the subject is able to complete the **CCI** questionnaire on their personal electronic device while on site.
- 5) Subjects should complete the DSQ daily after the last meal of the day. If Question 1 is answered “No,” the subject should answer the Solid Food Question ([Appendix 2](#)) after the DSQ is completed and submitted. The site is responsible for monitoring compliance throughout the duration of the study and discussing compliance during study visits.

Table 1 Notes cont.

- 6) On Day -2 (2 days before Day 1), on Day 15 (approximately 2 weeks after the first dose), and on Day 29 (approximately 4 weeks after the first dose), subjects will self-administer the CCI [REDACTED] after they submit the DSQ (and Solid Food Question, if applicable). On Day 15 and Day 29, subjects will also self-administer the CCI [REDACTED] after the DSQ, Solid Food Question (if applicable), and CCI [REDACTED].

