- 15) During the Screening EGD and Day 169 EGD, severity will be evaluated using the EoE Reference Score for Endoscopic Abnormalities per the study histology manual.
- 16) Please see the study central laboratory manual for collection, processing, and shipment instructions. If possible, samples should be shipped on the same day as collection.
- 17) Blood for serology (Hepatitis B surface antigen, Hepatitis C antibody, Hepatitis B core antibody, and HIV) will be obtained during screening.
- 18) For female subjects, blood will be obtained during screening to test for hCG (pregnancy) and FSH (post-menopausal status).
- 19) Blood for total serum IgE will be obtained on Days 1 (predose), 85 (predose), and 169 or ET, if subject early terminates before Day 169.
- 20) Blood for CBC with differential will be obtained at all study visits. On Days 1, 29, 57, 85, 113, and 141, blood will be drawn twice (predose and 1-hour postdose). For every CBC with differential blood collection except screening and Day 1 (predose), the blood count results will be blinded to the Sponsor and the site. The safety monitor may request an unscheduled CBC with differential. Blood counts from Day 197 will be used to determine if extended follow-up is needed.
- 21) Blood for chemistry will be obtained during screening, predose on dosing days (Days 1, 29, 57, 85, 113, 141), and on Days 169 and 197 (or ET).

Table 1 Notes cont.

- 22) Blood for PK will be obtained on Days 1, 8, 15, 29, 57, 85, 113, 141, 169, and 197 (or ET). Blood will be drawn predose on Days 1, 29, 57, 85, 113, and 141.
- 23) Blood for ADA will be obtained predose on Days 1, 29, 57, 85, 113, and 141, on Day 197 (or ET), and in the event of a suspected immunogenicity-related AE.
- 24) Blood for exploratory analysis will be obtained during screening and on Days 15, 169, and 197 (or ET).
- 25) If an infusion-related reaction results in infusion interruption or cessation, blood for exploratory safety analyses will be obtained within 1–2 hours of symptom onset.
- 26) Urine for standard urinalysis will be obtained during screening, as needed (if warranted in the opinion of the Investigator or Subinvestigator), and on Day 197 (or ET).
- 27) For females of childbearing potential, urine for dipstick pregnancy test will be collected, tested, and results confirmed predose on Days 1, 29, 57, 85, 113, and 141.

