11.4.3 Urinalysis

Urine will be obtained for urinalysis during screening, as needed (if warranted in the opinion of the Investigator or Subinvestigator), and on Day 197 (or ET). The urine sample will be processed and shipped in accordance with the central laboratory manual and laboratory kit instructions. The central laboratory will analyze the urine sample for specific gravity, pH, protein, glucose, ketones, blood, and leukocyte esterase.

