12.5 Day 15 (± 2)

- 1) Document any changes to health status.
- 2) Document any changes to concomitant medications.
- 3) Document any changes to baseline diet.
- 4) Collect vital signs.
- 5) Perform symptom-directed physical exam, as needed.
- 6) Collect the following samples for the central laboratory:
 - a) CBC with differential
 - b) Pharmacokinetics
 - c) Blood for exploratory analysis
 - d) Urinalysis, if warranted in the opinion of the Investigator or Subinvestigator

12.6 Day 29 (± 3) – Dose 2

- 1) Pre-Infusion:
 - a) Confirm continued eligibility.
 - b) CCI to be self-administered by the subject via their personal electronic device.
 - c) Document any changes to health status.
 - d) Document any changes to concomitant medications.
 - e) Document any changes to baseline diet.
 - f) Determine body weight.
 - g) Collect vital signs.
 - h) Perform symptom-directed physical exam, as needed.
 - i) Collect the following samples for the central laboratory:
 - CBC with differential
 - Chemistry
 - Pharmacokinetics
 - Anti-drug antibodies
 - Urinalysis, if warranted in the opinion of the Investigator or Subinvestigator
 - j) Perform urine pregnancy test (if subject is of childbearing potential).
 - k) Enter the subject's PID and body weight in the IRT system for IP kit assignment.
 - l) The pharmacist will receive an email with PID, body weight, and kit number.
 - m) The study pharmacist will prepare study drug using the weight obtained at the visit. The final combined volume of the IV bag of study drug + 0.9% NaCl will be **120 mL**.

Note: 100 mL of the calculated dose of study drug will be administered to the subject. The extra 20 mL is to be used to prime the IV infusion line during the preparation of the IV line at the bedside or to be left over in the infusion bag.
- 2) During the Infusion of Study Drug:
 - a) Infuse 100 mL of study drug over at least 3 hours using an infusion pump per the instructions and infusion rate schedule in the Administration of Investigational Product section of the Pharmacy Manual. Record the start and stop times of the infusion including any times the infusion is interrupted.
 - b) Collect vital signs 15 (± 5) minutes after the start of infusion.

- c) Perform symptom-directed physical exam, as needed.

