- 13) Blood for ADA will be obtained predose on Day 176 and on Day 372 (or ET). For Days 204, 232, 260, 288, and 316, blood for ADA will be obtained only if a suspected immunogenicity-related AE occurs.
- 14) Blood for exploratory analysis will be obtained predose on Day 316 and on Day 372 (or ET).
- 15) Blood for exploratory safety analyses will only be obtained within 1–2 hours of symptom onset if an IRR results in infusion interruption or cessation.
- 16) Urine for urinalysis will be obtained predose on Day 176, as needed (if warranted in the opinion of the Investigator or Subinvestigator), and on Day 372.
- 17) For females of childbearing potential, urine will be collected, tested, and pregnancy result confirmed predose on Days 176, 204, 232, 260, 288, and 316.

Table 5 Notes cont.

- 18) The day before the first open-label AK002 dose (12–24 hours prior to the infusion start time), subjects will self-administer oral prednisone premedication at a dose of 40 mg if body weight is <40 kg, 60 mg if body weight is \geq 40 kg and <60 kg, or 80 mg if body weight is \geq 60 kg. This dose of prednisone premedication should be recorded in the Concomitant Medications CRF of both the AK002-014 treatment period database and the AK002-014 OLE period database.
- 19) Open-label AK002 will be administered as a single peripheral IV infusion over \geq 4 hours on Day 176, over \geq 3 hours on Day 204, and over \geq 2 hours on Days 232, 260, 288, and 316. Refer to the Pharmacy Manual for detailed administration and infusion rate schedule instructions.
- 20) Subjects will remain under observation at the site for at least 1 hour after the end of each infusion. In the event of an IRR, the subject may require prolonged observation (>1 hour or until the symptoms resolve), as per Investigator discretion. Subjects will also be instructed to immediately contact the study doctor if any reactions occur after discharge.
- 21) If a new or worsening symptom (or clinically significant finding) is observed or reported, the Investigator or designee will determine whether a symptom-directed physical examination is warranted. Symptom-directed physical examinations will be performed if warranted (per the Investigator or designee judgment) and may be performed at any time or multiple times during a visit (predose, during infusion, and/or postdose).

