**9.3 Appendix 3: List of Tables, Listings, and Figures cont.**

Table 14.3.1.1	Overview of Treatment-Emergent Adverse Events (Safety Population)
Table 14.3.1.2	Treatment-Emergent Adverse Events by Preferred Term: Subject Incidence (Safety Population)
Table 14.3.1.3	Treatment-Emergent Adverse Events by System Organ Class and Preferred Term: Subject Incidence (Safety Population)
Table 14.3.1.4	Treatment-Emergent Adverse Events by System Organ Class, Preferred Term, and Maximum Severity: Subject Incidence (Safety Population)
Table 14.3.1.5	Treatment-Emergent Adverse Events by System Organ Class, Preferred Term, and Relationship to Study Drug: Subject Incidence (Safety Population)
Table 14.3.1.6	Treatment-Emergent Adverse Events Leading to Study Drug Discontinuation by System Organ Class and Preferred Term: Subject Incidence (Safety Population)
Table 14.3.1.7	Treatment-Emergent Serious Adverse Events by System Organ Class and Preferred Term: Subject Incidence (Safety Population)
Table 14.3.1.8	Treatment-Emergent Adverse Events of Special Interest by System Organ Class and Preferred Term: Subject Incidence (Safety Population)
Table 14.3.2.1	Hematology: Change from Baseline by Visit (Safety Population)
Table 14.3.2.2	Blood Chemistry: Change from Baseline by Visit (Safety Population)
Table 14.3.2.3	Hematology: Shift from Baseline Classification by Visit (Safety Population)
Table 14.3.2.4	Blood Chemistry: Shift from Baseline Classification by Visit (Safety Population)
Table 14.3.2.5	Urinalysis: Change from Baseline by Visit (Safety Population)
Table 14.3.3	Summary of Vital Signs by Visit (Safety Population)

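### Urinalysis change is tabulated by visit, but no double-blind visit between screening and Day 197 has a routine urinalysis, so the rows are selected subsets

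*SAP*

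**What the plan says.** **Collection.** Protocol 11.4.3 reads: "Urine will be obtained for urinalysis during screening, as needed (if warranted in the opinion of the Investigator or Subinvestigator), and on Day 197", or at ET. Table 1 note 26 gives the same rule. The visit lists in Protocol 12.3 and 12.5 to 12.10 (Days 1, 15, 29, 57, 85, 113 and 141) carry the condition "Urinalysis, if warranted in the opinion of the Investigator or Subinvestigator". The Day 169 list in 12.11 omits urinalysis, although Table 1 puts a footnoted mark there. Section 12.13 lists urinalysis at ET without condition.

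**Open-label entrants.** Table 1 says "Day 197 visit does not apply to subjects in OLE period". For these subjects Table 5 note 16 begins "Urine for urinalysis will be obtained predose on Day 176, as needed" and ends with Day 372. I read it as three occasions (Day 176 predose, as needed, Day 372), parallel to note 26.

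**Analysis.** Urinalysis is a named safety endpoint (Protocol 6.1, SAP 2.4). SAP 6.15.2 says "For quantitative laboratory parameters, both actual values and change from baseline values will be summarized at each visit", and Protocol 15.8 names urinalysis in the same plan. SAP Table 6 defines urinalysis rows for Days 1, 15, 29, 57, 85, 113, 141, 169 and 197. SAP Appendix 3 lists Table 14.3.2.5, "Urinalysis: Change from Baseline by Visit (Safety Population"). It is the only urinalysis summary table listed; the shift tables cover hematology and chemistry.

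**The concern.** A by-visit change table assumes that each row represents the arm at that visit. For hematology and chemistry the schedule supports this. For urinalysis it does not: whether a subject appears in a row depends on an investigator's decision, on early termination or on open-label entry.

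A reader who sees Days 15 to 169 laid out by arm would naturally read a course over treatment and a contrast with placebo. Either reading could produce a false signal or false reassurance on a named safety endpoint. The first safety analysis uses data through Day 169 (Protocol 16.4, SAP 5.6). At that cut-off the double-blind schedule has produced no routine post-baseline urinalysis except at ET.

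**Working it through.** The plan states no figure on this point. Its dropout assumption, used below, is consistent with its sample size: 86 / (1 − 0.14) = 100 per arm (Protocol 15.2, SAP 3.6).

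**Step 1: place each collection in SAP Table 6.** ET day = day of last dose + 28 ± 3 (Protocol 12.13). After a last dose on Day 1, that is 1 + 28 − 3 = 26 to 1 + 28 + 3 = 32; the other doses follow in the same way. SAP 5.2 slots ET and unscheduled values into the windows.

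| Table 6 row | Window | What can fall in it |
|---|---|---|
| Day 1 | Predose, Day 1 | As needed only |
| Day 15 | Day 1 postdose to 18 | As needed; an unusually early ET visit |
| Day 29 | 21–42 | As needed; ET on Days 26–32 |
| Day 57 | 43–70 | As needed; ET on Days 54–60 |
| Day 85 | 71–98 | As needed; ET on Days 82–88 |
| Day 113 | 99–126 | As needed; ET on Days 110–116 |
| Day 141 | 127–154 | As needed; ET on Days 138–144 |
| Day 169 | 155–186 | As needed; ET on Days 166–172; possibly Day 176 predose |
| Day 197 | 187 to end of study | Routine Day 197 samples of subjects not in the open-label period; late ET |

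Day 176 ± 3 is Days 173–179, and the tolerated ± 7 (Table 5 note 27) gives Days 169–183. Both lie inside the Day 169 window. Days 19 and 20 fall in no window.

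**Step 2: how many ET samples.** At 14% dropout, 0.14 × 300 = 42 subjects, or 14 per arm. Spread evenly over the six rows from Day 29 to Day 169 (an assumption), that is 14 / 6 ≈ 2.3 per arm per row, and fewer if ET visits are missed.

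**Step 3: how many routine end samples.** Per 100 randomised, 100 × (1 − 0.14) = 86 complete. The documents give no roll-over rate for this trial, so I assume 70% to 90%; more than 90% continued in the Phase 2 gastritis/duodenitis study.
- Open-label entrants, with Day 176 predose urine: 86 × 0.70 = 60.2 to 86 × 0.90 = 77.4.
- Subjects with a Day 197 sample: 86 × 0.30 = 25.8 to 86 × 0.10 = 8.6.

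**Step 4: two rules that add to the mixing.** When several values share a window, SAP 5.2 takes the one nearest the target day, so an as-needed Day 169 sample would displace the same subject's routine Day 176 sample. SAP Table 2 takes the latest pre-dose value as baseline, so an as-needed Day 1 sample displaces the screening one. For that subject the Day 1 row of Table 6 then shows a change of zero by construction.

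**Step 5: can the routine samples be pooled?** Nominal time since last dose is 28 days at ET, 176 − 141 = 35 days at Day 176 and 197 − 141 = 56 days at Day 197. Day 176 samples also follow prednisone premedication taken 12 to 24 hours before the infusion (Protocol 19.12.4). One pooled row would mix these conditions.

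**The case against.** A reader might infer that every on-treatment row consists of for-cause samples. The documents do not support that. Urinalysis at ET is unconditional in 12.13, and ET values enter the Day 29 to Day 169 rows. If Day 176 predose data are used, the Day 169 row could be mostly routine samples. This corrects the mechanism but not the conclusion: ET samples are selected by discontinuation, and Day 176 samples by open-label entry.

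A reader might also infer a bias for or against AK002. That is not supported either. The documents give no as-needed sampling rate by arm, and none of the infusion-reaction symptoms in Protocol 13.4 is urinary. Some rows may simply be near-empty.

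The safeguards are real. No formal inference is made on safety parameters (Protocol 15.1), summaries show n (SAP 5.1), clinically significant post-dose laboratory values are recorded as AEs (Protocol 11.4), and a full urinalysis listing is planned. The Day 1 urine is collected before randomisation (Protocol 12.3), so a displaced baseline cannot depend on arm; it only makes baselines less uniform. SAP 6.15.2 is also general laboratory wording, and the specific support lies in Table 6 and Table 14.3.2.5. All of this limits the consequence. None of it makes the by-visit rows readable, because nothing in the plan labels as-needed samples or keeps them out of the table.

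**Conclusion.** The point holds as a low-cost improvement. No urinalysis row from Day 1 to Day 169 represents its arm, and the Day 197 row covers only subjects who did not enter the open-label period (about 9 to 26 per 100 randomised under the assumed roll-over). The rows cannot be read as a trend or as a comparison of arms. The size and direction of any distortion cannot be stated from the documents.

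This rests on three things: the 14% planning dropout; the assumed 70% to 90% roll-over, which sizes only the Day 176 and Day 197 split; and double-blind data only in the Day 197 row. Two matters are left open by the plan:
- Whether Day 176 predose laboratory data belong to the double-blind analysis set. SAP Table 5 has a Day 176 window for PK and ADA; Table 6 has none for urinalysis.
- Whether urine is required at ET before Day 169. Table 1 note 32 sends ET after Day 29 and before Day 169 to the Day 169 schedule, where urinalysis is not routine, while note 26 and section 12.13 call for it at ET.

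**What to change.** In SAP 6.15.2, Table 6 and Table 14.3.2.5:

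- Limit the urinalysis change-from-baseline summary to scheduled collections, with the routine screening sample as baseline.
- Give separate rows, each with n, for ET, Day 176 predose (open-label entrants, before the first open-label dose) and Day 197. Do not pool them.
- Drop the Day 1 to Day 169 visit rows for urinalysis, and report as-needed samples in the listing.
- State whether Day 176 predose laboratory data belong to the double-blind analysis set. Without them, that row cannot be produced.
- Reconcile Table 1 note 32 with note 26 and Protocol 12.13 on urinalysis at ET.

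The SAP supersedes the protocol's statistical methods, so the table changes need only SAP and shell wording; reconciling the ET passages may also need a protocol clarification. No data are lost, since the full listing is already planned. The costs are that for-cause values appear only in the listing and, if clinically significant, as AEs; that urinalysis departs from the study-wide baseline rule; and that the Day 197 row cannot be complete at the provisional lock.
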